9.7.2 Secondary Objectives

The analysis of the secondary endpoints will be descriptive, and no hypothesis testing is planned.

Hazard ratios and corresponding two-sided 95% confidence interval for all secondary endpoints will be estimated using the same meta-analytic approach described for primary endpoint.

9.7.3 Exploratory Objectives

Not Applicable

9.8 Quality Control

Not Applicable, as quality control was performed within the clinical trial protocols of the data sources.

9.8.1 Database Retention and Archiving of Study Documents

Not Applicable. As no investigators are directly involved in this study, database retention and archiving of study documents by investigators is not applicable for this meta-analysis of existing clinical trials.

9.8.2 Registration of Study on Public Website

This study will be registered in the EU PAS Register.

9.9 Limitations of the Research Methods

The following aspects may affect the consistency and robustness of the evaluation of the safety question of interest:

Low prevalence of the disease and low rate of MACE reports: Recent studies in Europe estimate that the prevalence of HCM ranges from 4-7 per 10,000. 11,12,13,14 As the proportion of patients with symptomatic disease is approximately 48-61% in oHCM 15,16,17,18 and 33-35% 17,18 in nHCM, prevalence of symptomatic obstructive HCM in the adult population is < 5 in 10,000. Traditional MACE events (CV-death, non-fatal MI, non-fatal stroke) occur with a low frequency (approximately 1.5-2% per year in registries and cohorts) in HCM population. 3,19,20,21,22,23 Consequently, and to capture a wider range of events that could be considered clinically meaningful, the CV outcome definition was expanded from traditional MACE to e-MACE.

Varied follow-up in randomized, placebo-controlled trials: Mavacamten is intended for chronic use, but due to various constraints in the clinical development (e.g., the expected onset of treatment effect, and ethical considerations regarding the long-term exposure to placebo in symptomatic HCM patients) the available mavacamten RCTs have placebo-controlled periods of various duration. Considering the duration of the placebo-controlled double-blind period and low overall event rate, the number of events is expected to be low in each individual study. Consequently, small changes in the data can cause significant changes in the results. This problem could persist even after pooling data from many studies. Thus, as supplementary analysis, it is proposed to estimate exposure-adjusted incidence rates (from pooled data) for mavacamten and the placebo arm (within placebo-controlled double-blind period) to account for potentially different exposures.

Generalizability: Like all clinical trials, those included in the meta-analysis utilized specific inclusion/exclusion criteria that are more specific than the approved indication. Further, the RCTs included as data sources in the meta-analysis are conducted mostly in academic cardiac centers, some specializing in cardiomyopathy management, with a thorough and close follow up of patients which allows gathering of robust safety data, which may differ from clinical practice. However, the studies selected for the meta-analysis are representative of the broad symptomatic HCM population for which mavacamten is currently approved in the EU (oHCM) or may be approved on the basis of the ODYSSEY-HCM study (nHCM). Consequently, the patient population of this meta-analysis is considered appropriate for the purpose of CV risk evaluation based on the mechanism of action of the drug and similarities in the disease pathophysiology across the different study populations in clinical practice, as was accepted by CHMP (EMEA/H/C/005457).

Limitations of statistical methods: First, as the event rate is low, the study may encounter trial(s) with no events in one or both groups, as was observed for VALOR-HCM. In this situation the problem of monotone likelihood can be encountered, and the standard Cox Proportional Hazards method will have trouble with convergence. Even when the model does converge, the resulting estimates are often imprecise and have large standard errors. Details of statistical method(s) to address this will be provided in the SAP. Second, the model assumes proportional hazards i.e., hazard functions for any two individuals are proportional at any point in time and the hazard ratio does not vary with time. Any departure from proportional hazards will be assessed and additional analysis may be performed to account for non-proportionality. Third, the total number of events in four of five studies is either known or expected to be small (less than 12 events). Therefore, the ability to test for heterogeneity across studies may be limited. ²⁴ The results from the individual studies will be assessed for qualitative consistency to ensure meta-analysis proceeds in a scientific manner and to aid in the interpretation of the results from the meta-analysis.

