EXPLORER-HCM (MYK-461-005) (placebo-controlled, double-blind period: 2018-2020; completed) ⁶ [refer to CSR in eCTD sequence number 0000]	Phase 3, double-blind, randomized 1:1, placebo-controlled, multicenter, international, parallel-group study to evaluate the safety, tolerability, and efficacy of mavacamten compared with placebo in adults ≥ 18 years with symptomatic oHCM	The starting dose of mavacamten was 5 mg once daily. At Week 8 and Week 14, mavacamten dose was up-titrated for individual subjects based on their mavacamten plasma concentration and pharmacodynamic (PD) responses at Week 6 and Week 12, respectively, and according to dose titration protocol. The permissible doses were 2.5 mg, 5 mg, 10 mg, and 15 mg.	 LVOT peak gradient ≥ 50 mmHg during screening as assessed by echocardiography at rest, after Valsalva maneuver or post-exercise and VLVOT gradient ≥ 30 mmHg (confirmed by echocardiography core laboratory interpretation). NYHA Class II or III symptoms at screening Background HCM therapy (e.g., beta-blocker, verapamil, or diltiazem) is allowed. 	A total of 251 subjects were randomized 1:1 into the study, including 123 subjects in the mavacamten group and 128 subjects in the placebo group. Subjects remained in the doubleblind period for 30 weeks followed by 8 weeks of double-blind study drug washout

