VALOR-HCM (CV-027-006) ⁷ (placebo-controlled, double-blind period: 2020—2022; completed) [refer to primary CSR in eCTD sequence number 0005]	Phase 3, randomized, double-blind, placebo-controlled, multicenter study of adults ≥ 18 years with oHCM who meet 2011 ACCF/AHA criteria for SRT and have been referred for an SRT procedure.	The starting dose of mavacamten in this study was 5 mg once daily and subjects were evaluated for possible down-titration at Week 4 based on Valsalva LVOT < 30mmHg and up-titration at Weeks 8 and 12 to a maximum dose of mavacamten 15 mg based on the LVEF ≥ 50% and Valsalva LVOT gradient ≥30 mmHg dose titration protocol. The permissible doses were 2.5 mg, 5 mg, 10 mg, and 15 mg.	 Dynamic LVOT gradient at rest or with provocation (ie, Valsalva or exercise) ≥ 50 mmHg NYHA Class III or IV or subjects who are NYHA Class II with exertion-induced syncope or near syncope Mono- or combination therapy with beta-blockers, non-dihydropyridine calcium channel blockers, and/or disopyramide was allowed 	A total of 112 subjects were randomized 1:1 to mavacamten and placebo group, including 56 subjects in the mavacamten group and 56 subjects in the placebo group. Subjects remained in the doubleblind period for 16 weeks followed by active-controlled (Week 16 – Week 32) and long-term extension period (up to Week 128) where all subjects receive mavacamten.

Table 9.2.1-1: Overview of BMS (or partner)-sponsored Placebo-controlled Clinical Trials Included in the Meta-analysis

	anarysis			
Study	Study Design	Dosing Regimen	Study Population	Sample Size & Study Duration – Current Status

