EXPLORER-CN (LB2001-301) (placebo-controlled, double-blind period: 2020-2023; completed) [refer to protocol]	Phase 3, randomized, double-blinded, placebo-controlled, multicenter, parallel-group clinical study with a long-term extension to evaluate the efficacy, safety, and PK of mavacamten in Chinese adults with symptomatic oHCM	The starting dose of mavacamten in this study is 2.5 mg once daily (QD).: At Week 8, Week 14 and Week 20, mavacamten dose will be adjusted (increase, decrease, remain unchanged) for individual subjects based on their mavacamten plasma concentration and pharmacodynamic (PD) responses at Week 6, Week 12, and Week 18, respectively, and according to dose titration protocol. The permissible doses were 1 mg, 2.5 mg, 5 mg, 10 mg, and 15 mg.	 LVOT peak gradient ≥ 50 mmHg during screening as assessed by echocardiography at rest or after Valsalva maneuver (confirmed by echocardiography core laboratory interpretation). NYHA Class II or III symptoms at screening Background HCM therapy (e.g., beta-blocker, verapamil, or diltiazem) is allowed. 	Approximately 81 eligible participants were enrolled and randomized (2:1) to mavacamten and placebo group. Participants received mavacamten or matching placebo for 30 weeks in double blinded manner. After 30-week double-blinded placebo-controlled treatment, eligible participants receive mavacamten for additional 48 weeks (placebo group: switch from placebo to mavacamten, mavacamten group: maintain on mavacamten).

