9.7.1 Primary Objective

The primary analysis will include time to the first e-MACE event that occurs on-treatment during the placebo-controlled double-blind period for each study. Patients completing the placebo-controlled double-blind period without any events observed will be censored at the end of the placebo-controlled double-blind treatment period. Patients who prematurely discontinue study or discontinue treatment early without any events observed will be censored at the earliest occurrence of either the last contact date, treatment discontinuation date, or scheduled end of placebo-controlled double-blind treatment period.

The time to the first occurrence of an e-MACE event will be analyzed using a stratified Cox proportional hazards model⁹ with study as a stratification factor and treatment as a fixed effect, to provide the overall hazard ratio (HR) between mavacamten and placebo along with its associated 95% confidence interval.¹⁰

The primary endpoint null hypothesis will be rejected if the upper bound of the two-sided 95% confidence interval around HR, based on stratified Cox proportional hazards model, is less than 2.2. The primary estimand is defined below in Table 9.7.1-1.

Table 9.7.1-1: Estimand definition

	Estimand			
Endpoint Category	Endpoint	Analysis Population	Intercurrent Events	Population-level Summary
Primary objective is to assess the risk of e-MACE in mavacamten group compared to placebo, by evaluating the primary endpoint with a noninferiority margin of 2.2.				bo, by evaluating the
Primary endpoint	Time to first e-MACE event	Safety Analysis Population*	Patients who prematurely discontinue study (including non-CV death) or discontinue treatment, will be censored at the earlier of last contact date or treatment discontinuation date or scheduled end of placebo-controlled double-blind treatment period.	The time to the first occurrence of e-MACE events will be analyzed using a stratified Cox proportional hazards model.

^{*}Safety analysis population is defined as all randomized participants who received at least one dose of study drug with analyses conducted according to the actual treatment received

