9.10 Other Aspects

As supplementary analysis, pooled exposure-adjusted incidence rate (EAIR) by treatment group will be presented along with 95% confidence interval of the EAIR as appropriate.

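### The supplementary exposure-adjusted incidence rates are pooled by arm without regard to study, although EXPLORER-CN is randomised 2:1 and the other four studies 1:1

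*Protocol*

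**What the plan says.** Two places in the protocol describe the analysis. Under varied follow-up, Section 9.9 says "it is proposed to estimate exposure-adjusted incidence rates (from pooled data) for mavacamten and the placebo arm", as a way of allowing for differing exposure. Section 9.10 says "pooled exposure-adjusted incidence rate (EAIR) by treatment group will be presented along with 95% confidence interval of the EAIR as appropriate". Both call it supplementary. Neither mentions stratifying or weighting by study, and neither names a rate ratio, a rate difference or a test.

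The treatment comparison itself is specified differently. Section 9.7.1 uses a Cox model "with study as a stratification factor and treatment as a fixed effect, to provide the overall hazard ratio (HR"), and Section 9.7.2 carries that approach to the secondary endpoints.

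Table 9.2.1-1 gives the allocation. EXPLORER-CN was "randomized (2:1) to mavacamten and placebo group". EXPLORER-HCM, VALOR-HCM, MEMENTO and ODYSSEY-HCM are 1:1. The double-blind periods last 30 weeks (EXPLORER-HCM, EXPLORER-CN), 16 weeks (VALOR-HCM) and 48 weeks (MEMENTO, ODYSSEY-HCM).

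**The concern.** Dividing all events in an arm by all patient-years in that arm adjusts for total exposure, but not for which studies the exposure came from. With a common allocation ratio the study mix is the same in both arms, and this does no harm. With one study at 2:1 the mix differs: that study counts for more in the mavacamten rate than in the placebo rate. If its underlying event rate is unlike the others, the gap between the two pooled rates contains a study effect as well as any drug effect.

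Different rates are plausible from the protocol's own description. The trials cover obstructive and non-obstructive disease, patients referred for septal reduction, and a trial that excludes patients with an ICD. EXPLORER-CN is the one trial described as enrolling Chinese adults.

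At stake is how a safety report is read. Two rates side by side, each with a confidence interval, will be compared whether or not a ratio is printed beneath them, and they could differ somewhat from the stratified hazard ratio for a reason unrelated to the drug.

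**Working it through.** The protocol gives no rate, event total or power for this analysis, so there is no stated figure to reproduce. The check uses planned exposure.

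**Inputs (Table 9.2.1-1).** EXPLORER-HCM: "including 123 subjects in the mavacamten group and 128 subjects in the placebo group"; "Subjects remained in the doubleblind period for 30 weeks". VALOR-HCM: "including 56 subjects in the mavacamten group and 56 subjects in the placebo group", 16 weeks. EXPLORER-CN: about 81 patients at 2:1, taken as 54/27, 30 weeks. MEMENTO: 50/50, 48 weeks. ODYSSEY-HCM: about 420 at 1:1, taken as 210/210, 48 weeks.

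**Step 1: planned patient-years** = arm size × weeks / 52, with no dropout.

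| Study | Mavacamten | Placebo |
|---|---|---|
| EXPLORER-HCM | 71.0 | 73.8 |
| VALOR-HCM | 17.2 | 17.2 |
| EXPLORER-CN | 31.2 | 15.6 |
| MEMENTO | 46.2 | 46.2 |
| ODYSSEY-HCM | 193.8 | 193.8 |
| Total | 359.3 | 346.7 |

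The EXPLORER-CN share is 31.2/359.3 = 8.7% of mavacamten exposure and 15.6/346.7 = 4.5% of placebo exposure.

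**Step 2: pooled ratio with no drug effect.** Give every study the same rate in both arms, and let the EXPLORER-CN rate be k times a common rate in the other four. The ratio of pooled rates is (0.9133 + 0.0867k) / (0.9551 + 0.0449k), which does not depend on the common rate.

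| k | Pooled ratio |
|---|---|
| 0 | 0.956 |
| 0.5 | 0.979 |
| 1 | 1.000 |
| 2 | 1.040 |
| 3 | 1.077 |

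To put this in absolute terms, assume a common rate of 0.08 per patient-year (the protocol gives none). The pooled rates are then 7.31 against 7.64 per 100 patient-years at k = 0, and 9.39 against 8.72 at k = 3. At k = 3 EXPLORER-CN would have 0.24 × 46.7 = 11.2 events. Section 9.9 expects fewer than 12 in four of the five studies without naming them; EXPLORER-CN is taken to be one of the four.

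**Step 3: is it duration or allocation?** Without EXPLORER-CN, the four 1:1 studies give pooled ratios of 0.99 to 1.01 under the widely differing study rates tried, despite periods of 16 to 48 weeks. The distortion comes almost wholly from the 2:1 study.

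**Step 4: stratified alternative.** For study i let M and P be the patient-years and a and b the events on mavacamten and placebo, with T = M + P. The Mantel-Haenszel rate ratio is Σ(aP/T) / Σ(bM/T). With equal rates r in the two arms both sums equal Σ(rMP/T), so the ratio is exactly 1.00 whatever k is. The matching rate difference is Σ[(aP − bM)/T] / Σ(MP/T). A study without events adds 0 to the numerator and its MP/T to the denominator, so it stays in.

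**Step 5: practical effect.** In a Poisson simulation with no drug effect (200,000 runs per scenario, those with events in both arms kept), a crude 95% interval for the pooled ratio excluded 1 in about 4.6% of runs at k = 1, 5.0% at k = 0 and 5.5% at about k = 3.

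As an extreme bound, put 11 events in EXPLORER-CN, 12 in ODYSSEY-HCM and none elsewhere. At equal rates by arm, expected events are 7.33 + 6 = 13.33 on mavacamten and 3.67 + 6 = 9.67 on placebo. The pooled ratio is (13.33/359.3) / (9.67/346.7) = 1.33, and the simulated exclusion rate is about 9.2%.

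**The case against.** The strongest reply is that no comparison of these rates is planned. Each arm gets a rate and an interval for that rate, labelled supplementary, and the only planned treatment comparison is stratified by study. That is correct, and a reader who infers that the protocol commits to a crude rate ratio goes beyond the text. What remains is that pooling by arm is stated, and that the two rates will be read together.

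A second reply is that crude is an inference from pooled, and that Section 9.6 leaves analysis detail to the SAP, which is not at hand and may specify weights. This lowers the weight of the point but does not remove it: the protocol describes pooling by treatment group without study, in contrast to its stratified primary analysis.

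A third is that exposure-adjusted rates are worth having because a hazard ratio gives no absolute risk. Agreed; the point concerns how they are combined, not whether to report them.

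Two stronger readings are tempting and fail:

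- **Differing follow-up periods confound the pooled rates.** Step 3 shows that they do not when arms are balanced within study; unequal allocation together with unequal event rates is needed.
- **These rates are the only place where a study without events can contribute.** Section 9.9 raises that problem itself, names VALOR-HCM, and defers the method to the SAP.

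**Conclusion.** The point holds as a minor one. Pooling by arm across one 2:1 study and four 1:1 studies puts a known, avoidable allocation effect into the two supplementary rates. Its size is about −4% to +8% on the ratio scale for an EXPLORER-CN rate between 0 and 3 times that of the other studies. The 1.33 case needs three studies with no events at all and marks an outer bound, not an expectation. Sampling noise is the larger problem in ordinary scenarios.

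These figures assume no dropout, the 54/27 and 210/210 splits, a 52-week year, and (for the 0.96 to 1.08 range) a common rate in the other four studies. Discontinuation that differs by study and arm would change the shares by an amount that the protocol does not allow one to estimate.

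A reader might go on to infer that the non-inferiority conclusion is at risk. It is not: that decision rests on the study-stratified hazard ratio against 2.2, which does not use these pooled rates.

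**What to change.** In Sections 9.9 and 9.10, or in the SAP with a pointer from them:

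- Present the exposure-adjusted incidence rate by study and arm.
- Make the between-arm summary a study-stratified rate difference (for example Mantel-Haenszel, weighted by person-time) over all five studies, including any without events, and the matching rate ratio, each with a 95% confidence interval.
- State that any crude pooled rate is descriptive and not for comparison between arms.

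The cost is wording, a few lines of code and slightly more output. No new data are needed, and the primary analysis does not change. It is best settled before ODYSSEY-HCM and MEMENTO are unblinded, which Section 9.7 projects by 1Q 2026.

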9.10 Other Aspects

As supplementary analysis, pooled exposure-adjusted incidence rate (EAIR) by treatment group will be presented along with 95% confidence interval of the EAIR as appropriate.

9.10.1 Strengths of Research Methods

The meta-analysis includes all randomized, placebo-controlled studies of mavacamten that have been completed, initiated or planned for initiation prior to the end of 2023, which results in five RCTs that qualify for inclusion (see Section 9.2.2). Utilizing data from RCTs ensures rigorous collection of safety data in a controlled manner in line with the EMA Reflection paper on assessment of cardiovascular safety profile of medicinal products, as these studies were designed and conducted to high standards in respect of assessment of CV outcomes.

Despite some differences in the design and study population in these five studies, each study was or will be adequately controlled and conducted in a well-defined population of adult patients with symptomatic oHCM or nHCM, using thorough inclusion/exclusion criteria in the individual study protocols (e.g., cardiac functional and physiological parameters, as well as permitted background therapy). These study populations were chosen as representative of the broad HCM patient population and considered appropriate for the purpose of CV risk evaluation based on the mechanism of action of the drug and similarities in the disease pathophysiology across the different study populations in clinical practice. Consequently, the trials' results, and the results of the meta-analysis, can be extrapolated to the more broadly defined population of patients with symptomatic HCM.

10 PROTECTION OF HUMAN SUBJECTS

Not Applicable.

10.1 Ethics Committee Review and Informed Consent

Not applicable. This study does utilize previously collected, de-identified data, and does not require review and approval by ethics committees or informed consent.

10.1.1 Ethics Committee Review

Not Applicable.

10.1.2 Informed Consent

Not Applicable. This study does not require that informed consent is obtained from patients.

10.2 Confidentiality of Study Data

The confidentiality of records that could identify patients within the database must be protected, respecting the privacy and confidentiality rules in accordance with the applicable regulatory requirement(s). No identifying information will be provided.

11 MANAGEMENT AND REPORTING OF ADVERSE EVENTS/ADVERSE REACTIONS

The design of this study is characterized by secondary use of data previously collected for other purposes. Therefore, for this study the submission of suspected adverse reactions in the form of Individual Case Safety Reports is not required.

11.1 Adverse Event Collection and Reporting

11.1.1 Adverse Event Collection

All patient-level MACE adverse events have been and will be collected within the individual clinical trials and will be analyzed and reported in aggregate in the final study report of the meta-analysis.

11.1.2 Adverse Event Reporting

Expedited individual case safety reporting is not applicable (secondary use of data).

12 PLANS FOR DISSEMINATING AND COMMUNICATING STUDY RESULTS

Study progress reports will be included in the PBRER in accordance with EURD list, starting within 1 year after protocol approval by PRAC (see Section 6). Progress reports will contain status updates of the data sources and any relevant amendments pertaining to the data sources.

The final study report will include all results of this meta-analysis described in the SAP.

